7.2 PRIMARY SAFETY ENDPOINT

The study's primary safety endpoint is the proportion of subjects in the Safety Population who experience either major stroke or death within 30 days, or major ipsilateral stroke or neurological death 31 days through 12 months post procedure. CEC-adjudicated data will be used for this analysis.

The primary safety hypotheses are:

$$H_{S0}: \pi_S \geq 0.25$$

$$H_{S1}: \pi_S < 0.25$$

The null hypothesis (H_{S0}) for this endpoint states that the true proportion of subjects treated with the FRED Device who experience neurologic death or major ipsilateral stroke one-year post-treatment is equal to or higher than 25%. The alternative hypothesis the FRED trial aims to demonstrate is that the true proportion of subjects treated with the FRED Device who experience neurologic death or major ipsilateral stroke one-year post-treatment is actually lower than 25%.

Using the noninformative prior

$$\pi_S \sim \text{Beta}(1,1)$$

the posterior distribution for the primary safety endpoint event rate will be

$$\pi_S | S, n \sim \text{Beta}(1 + S, 1 + n - S)$$

where n is the number of evaluable subjects and S is the number of subjects who meet the safety endpoint. The point estimate of the posterior distribution of the primary safety endpoint will be presented with its lower 95% credible bound, as well as the posterior probability of the alternative hypothesis H_{S1} . If the posterior probability exceeds 0.95, the primary safety endpoint will have been met

The supportive analysis (second OPC set) will be conducted for both primary efficacy and primary safety using more restrictive performance goals identified from a revised set of literature analysis and presented to FDA on 16 February 2017. The format of this analysis will be a Bayesian design identical in form to the above except that the performance goals will be 0.46 for efficacy and 0.15 for safety. Details of the resulting analyses and associated power are as below, from which it can be seen that the study is sufficiently powered at the final enrolled and treated count of 140.

	Efficacy		Safety	
	Original	Revised	Original	Revised
Significance level, alpha	0.05	0.025	0.05	0.025
1 or 2-sided test	1	1	1	1
Null: OPC, p_0	0.45	0.46	0.25	0.15
Alternative: FRED, p_A	0.58	0.60	0.15	0.06
Power (%)	90	90	90	92
N	140	140	140	140

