5.2 Study Hypothesis

The safety and effectiveness of the FRED meets similar performance goal as that which was identified from a comprehensive analysis of the peer-reviewed published literature reporting the safety and efficacy of endovascular treatment of intracranial aneurysms with flow-diverter devices.

Efficacy hypotheses

The study is designed to compare the rate of the primary efficacy endpoint to a performance goal. The null and alternative hypotheses are:

Null hypothesis: $H_0: \pi_e \leq 45\%$

Alternative hypothesis: $H_A: \pi_e > 45\%$

where π_e is the proportion of subjects that are successes for the primary efficacy endpoint.

Safety hypotheses

The study is designed to compare the rate of the primary efficacy endpoint to a performance goal. The null and alternative hypotheses are:

Null hypothesis: $H_0: \pi_s \geq 25\%$

Alternative hypothesis: $H_A: \pi_s < 25\%$

where π_s is the proportion of subjects with primary safety endpoint events.

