The primary safety outcome is the percent of subjects who experience death or major stroke within 30 days of the implant or death due to a neurological cause or major ipsilateral stroke through 12 months post implant. The study is designed to compare the primary safety percent to an independently derived performance goal, which is 25% for safety. The null and alternative hypotheses are:

Null hypothesis: $P_s \geq 25\%$

Alternative hypothesis: $P_s < 25\%$,

where P_s is the proportion of subjects with primary safety endpoint events.

The performance goal used in the P100018 SSED of the Pipeline PUFs study was 20%. However, the definition used in the PUFs study did not include all death and major stroke within 30 days, only death of neurologic cause and major ipsilateral strokes, and it was only evaluated through 180 days, not 12 months. For this reason, the performance goal utilized here is slightly higher. The primary safety endpoint in this study has not been used or reported as such previously, so the magnitude of the effect of this change is unknown. For the purposes of the current study a conservative 5% adjustment is used, resulting in a 25% performance goal (20% from above + 5% conservative adjustment). Should the FRED primary safety endpoint percent equal 15%, then the sample size of $N=155$ subjects would reject the null hypothesis with >80% power and one-sided 5% alpha level.

Statistical Methods for Primary Endpoints

The primary safety and effectiveness endpoints will be analyzed using Bayes models (OpenBUGS). The proposed model is a beta-binomial model that assumes that the outcome is a Binomial variable and a uniform prior on the probability of event.

Likelihood:

The likelihood is constructed based on distributional assumptions on the safety and efficacy results of the FRED system.

With N_e and N_s being the number of evaluable subjects for the Efficacy and Safety endpoints, respectively, the number of subjects that are successes for the primary efficacy endpoint, y_e , and the number of subjects with primary safety endpoint events are assumed to follow Binomial distribution with respective rates π_e and π_s . Thus,

$$y_e \sim \text{Binomial}(\pi_e, N_e) \text{ and } y_s \sim \text{Binomial}(\pi_s, N_s).$$

Prior Distributions:

Uninformative prior distributions are assumed for the efficacy and safety rates. More precisely,

$$\pi_e \sim \text{Beta}(1,1) \text{ and } \pi_s \sim \text{Beta}(1,1).$$

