3.2 PRIMARY ENDPOINTS

Primary Safety Endpoint:

The primary safety endpoint is the proportion of subjects who experience one or more of the following:

- a. death or major stroke within 30 days post procedure
 - b. neurological death or major ipsilateral stroke within 12 months post procedure
- ✦ *A major stroke is defined as a new neurological event that persists for > 24 hours and results in a ≥ 4 -point increase in the NIHSS score compared to baseline or compared to any subsequent lower score.*
 - ✦ *A major ipsilateral stroke is defined as that occurring within the vascular distribution of the stented artery*
 - ✦ *Neurologic death is defined as a death which has been adjudicated by the independent clinical events committee to have directly resulted from a neurologic cause*

Primary Effectiveness Endpoint:

Proportion of subjects with complete occlusion of the target aneurysm utilizing the Raymond Scale and $\leq 50\%$ stenosis of the parent artery at the target IA at 12 months as assessed by angiography and in whom an alternative treatment of the target IA had not been performed within 12 months post-FRED placement; where an alternative treatment is defined as re-treatment of the target aneurysm with an alternative treatment modality including open repair, endovascular placement of an additional stent or treatment of In-stent Stenosis observed at the 180 day or 12 month follow-up time-points or at an unscheduled study follow up visit.

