6.2 CRITERIA FOR SUCCESS FOR PRIMARY ENDPOINT ANALYSES

Primary efficacy and safety will be assessed by employing a Bayesian approach. Bayesian statistics are a principled approach for learning from evidence as it accumulates (FDA 2010, FDA guidance for industry and FDA staff guidance for the use of Bayesian statistics in medical device clinical trials, FDA CDRH CBER, February 5, 2010).

For the primary endpoints, the criterion for success is based on the posterior probability of the alternative hypothesis. The FRED device will be declared efficacious if the one-sided 95% lower

credible limit is at least 45%. The performance goal was obtained from a formal comprehensive literature review and meta-analysis of results from studies of flow diverters to treat patients matched to the FRED study subjects during the first year after treatment. Similarly, the FRED will be declared safe if the one-sided 95% upper credible limit is at most 25%. The performance goal used in the P100018 SSED of the Pipeline PUFs study was 20%.

However, the definition used in the PUFs study did not include all death and major stroke within 30 days, only death of neurologic cause and major ipsilateral strokes, and it was only evaluated through 180 days, not 12 months. For this reason, the performance goal utilized here is slightly higher. The primary safety endpoint in this study has not been used or reported as such previously, so the magnitude of the effect of this change is unknown. For the purposes of the current study a conservative 5% adjustment is used, resulting in a 25% performance goal (20% from above + 5% conservative adjustment).

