7 ENDPOINT ANALYSES

7.1 PRIMARY EFFICACY VARIABLE

The primary efficacy endpoint is the percent of subjects in the ITT population with complete occlusion (defined as Raymond class I) without clinically significant stenosis (defined as $\geq 50\%$ stenosis) of the parent artery at the target IA based on core lab evaluations at the 12-month follow-up angiography and in whom an alternative treatment of the target IA had not been performed post-FRED placement. An alternative treatment is defined as re-treatment of the target aneurysm with an alternative treatment modality including open repair, endovascular

placement of an additional stent or treatment of In-stent Stenosis observed at the 180-day or 12 month follow-up time-points or at an unscheduled study follow up visit.

The primary efficacy hypotheses are:

$$H_{E0}: \pi_E \leq 0.45$$

$$H_{E1}: \pi_E > 0.45$$

The null hypothesis (H_{E0}) for this endpoint states that the true proportion of subjects treated with the FRED Device who achieve complete occlusion (Raymond class I) without clinically significant ($\geq 50\%$) stenosis of the parent artery 12 months post-treatment and without any subsequent alternative treatment is no higher than 45%. The alternative hypothesis the FRED trial aims to demonstrate is that the true proportion of subjects who achieve effectiveness success at 12 months is greater than 45%.

Using the prior

$$\pi_E \sim Beta(1,1)$$

the posterior distribution for the primary efficacy endpoint rate will be

$$\pi_E | E, n \sim Beta(1 + E, 1 + n - E)$$

where n is the number of evaluable subjects and E is the number of subjects who meet the efficacy endpoint. The point estimate of the posterior distribution of the primary efficacy endpoint will be presented with its lower 95% credible bound, as well as the posterior probability of the alternative hypothesis H_{E1} . If the posterior probability exceeds 0.95, the primary efficacy endpoint will have been met.

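### Do the narrower hypothesis wording and the lower credible bound in SAP 7.2 put the primary safety test at risk?

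*SAP*

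**What the plan says.** SAP 7.2 opens with the full endpoint: "either major stroke or death within 30 days, or major ipsilateral stroke or neurological death 31 days through 12 months post procedure", on adjudicated data from the clinical events committee. SAP 3.2 gives the same composite, whose first component is "death or major stroke within 30 days post procedure". Protocol 6.2 agrees: "death or major stroke within 30 days of the implant or death due to a neurological cause or major ipsilateral stroke through 12 months". Protocol 5.2 defines the tested parameter simply as "the proportion of subjects with primary safety endpoint events".

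SAP 7.2 then states the hypotheses in symbols, with a 25% boundary, and repeats them in prose. The prose null concerns subjects "who experience neurologic death or major ipsilateral stroke one-year post-treatment is equal to or higher than 25" per cent, and the prose alternative uses the same event set.

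On reporting, SAP 7.2 says: "The point estimate of the posterior distribution of the primary safety endpoint will be presented with its lower 95% credible bound". SAP 7.1 uses the same sentence for efficacy: "The point estimate of the posterior distribution of the primary efficacy endpoint will be presented with its lower 95% credible bound". The 7.2 sentence goes on to require the posterior probability of the alternative as well, and the next sentence makes a value above 0.95 the test of success.

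The SAP summary, SAP 4.3, SAP 6.2 and Protocol 6.2 all judge safety on the one-sided 95% upper bound against 25%.

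**The concern.** Two things look wrong in the section that sets out the primary safety test.

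First, the prose hypotheses leave out non-neurologic death and major stroke outside the stented territory during the first 30 days. What remains is the kind of event set that SAP 6.2 attributes to the earlier flow-diverter study with the 20% goal, which "did not include all death and major stroke within 30 days, only death of neurologic cause and major ipsilateral strokes". Its lack of those early events, together with its shorter follow-up, is the stated reason for raising the goal to 25%. Read literally, the sentences would hold a narrower endpoint to a goal that was relaxed partly because the endpoint is broader. That would favour the device.

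Second, a lower bound says nothing useful about whether an adverse event rate is acceptably low. A table built only from the bound named in 7.2 would not show the figure on which safety turns.

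If either slip reached the analysis, the study could test the wrong event set or report a bound that does not support its conclusion.

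**Working it through.** **Inputs.** All are from SAP 7.2 unless noted: Beta(1,1) prior; posterior Beta(1+S, 1+n−S); S is the number of subjects meeting the safety endpoint; success if P(π_S < 0.25 | data) > 0.95. Power table: n = 140; null 0.25, alternative 0.15, alpha 0.05 (original goal); null 0.15, alternative 0.06, alpha 0.025 (revised goal). The SAP summary also gives a cohort of 145, so both sizes are checked for the 25% goal.

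**Step 1: reproduce the stated power.** Find the largest S with P(π_S < p0 | S, n) > 1 − alpha, then take the binomial probability of that many events or fewer at the alternative rate.

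| Goal | n | Largest passing S | Upper bound at S | Upper bound at S+1 | Power | SAP figure |
|---|---|---|---|---|---|---|
| 25% | 140 | 26 | 24.65% | 25.43% | P(S ≤ 26 given 0.15) = 90.1% | 90% |
| 15% | 140 | 12 | 14.39% | 15.25% | P(S ≤ 12 given 0.06) = 92.1% | 92% |
| 25% | 145 | 27 | 24.59% | 25.34% | 90.6% | not given |

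For the 25% goal at n = 140, the chance of passing at a true rate of 25% is P(S ≤ 26 given 0.25) = 4.5%.

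**Step 2: which bound does the 7.2 rule use?** The posterior is continuous, so P(π_S < 0.25 | data) > 0.95 holds exactly when its 95% quantile, the one-sided 95% upper bound, is below 0.25. At n = 140:
- S = 26: posterior probability 0.959, upper bound 24.65%, pass.
- S = 27: posterior probability 0.937, upper bound 25.43%, fail.

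The two forms of the rule agree. The SAP says at most 25% in one place and below 25% in another, but no whole number of events gives an upper bound of exactly 25%, so this makes no difference either.

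**Step 3: does the lower bound enter the decision?** At 26 and 27 events the lower 95% bounds are 13.9% and 14.5%, which do not separate pass from fail. No section makes the lower bound a safety criterion. The stated power rules that reading out too. Requiring only that the lower bound be under 25% would pass up to 43 of 140. At a true rate of 15%, the expected count is 140 × 0.15 = 21 with standard deviation √(140 × 0.15 × 0.85) = 4.2, so 43 lies (43 − 21)/4.2 = 5.2 standard deviations above it. Power would be virtually 100%, not the stated 90%.

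**Step 4: which events are counted?** The only data entering the posterior are n and S. S is defined through the safety endpoint, and the endpoint is the full composite in the opening of SAP 7.2, SAP 3.2 and Protocol 6.2. The prose null describes itself as the null for this endpoint, so it points back to that definition. No formula or rule uses the shorter event list.

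**Step 5: will the upper bound be reported?** SAP 6.3 requires the relevant one-sided and two-sided 95% credible intervals for the primary endpoints, and SAP 4.3 says both kinds will be computed. SAP 4.3 and 6.2 identify the upper bound as the relevant one for safety. For the 15% goal, the two-sided interval contains its own upper limit.

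**The case for a change.** The strongest case for a change is that correct text elsewhere does not make 7.2 correct. The section gives two event sets for one parameter, and the shorter one resembles the comparator's definition closely enough to matter if someone copied it into the report. SAP 4.3 says credible-interval claims will be sought for labelling, so the hypothesis and the bound ought to be stated properly. The repair would be cheap: two sentences and one word.

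It stands that both slips are real. They are not artefacts of redaction or text extraction, and anyone reissuing the SAP for another reason could tidy them. What does not stand is any effect on the result. The labelling claims rest on the supportive two-sided analysis, whose interval includes the upper limit. The deciding posterior probability is reported by the same sentence that names the wrong bound. The success criteria section, SAP 6.2, states the correct bound and explains why the 25% goal belongs to the broader endpoint. A report author would have to overlook all of this to carry either slip through.

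**Conclusion.** These are clerical slips. The bound wording matches the efficacy section and was probably carried over from it; the prose hypotheses are a loose abbreviation of an endpoint defined correctly at the start of the same section. An analyst following the plan counts the full composite, applies the posterior-probability rule and reports the upper bound.

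The size of the effect is nil. The cut-offs stay at 26 of 140 for the 25% goal and 12 of 140 for the 15% goal, power stays at 90.1% and 92.1%, and type I error for the 25% goal stays at 4.5%.

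This rests on two assumptions: that S is counted by the endpoint definition, as its wording in 7.2 requires, and that the intervals promised in SAP 4.3 and 6.3 are produced. The documents give no figure for how many events the shorter wording would omit, and none is needed, because that wording does not govern the count. No change to the plan follows.

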7.3 MISSING DATA ANALYSES

Subjects are expected to comply with the follow-up schedule. Efforts to prevent missing data include, but are not limited to, a reminder for the scheduled 30-day, 180 days and 12-month follow-up, obtaining additional phone numbers or contact information for all subjects at the time of the procedure along with requesting permission to contact the subject's family members or care-givers, and collecting only necessary data to reduce the burden to subjects and investigators. In-depth site training and regular monitoring will also help to minimize missing data, and collaborating with the Investigators to ensure the subjects are committed to complying with all scheduled follow-up visits.

Subject compliance with required follow up will be tabulated and reported as proportions. Subjects who withdraw from the study will be tabulated with the reasons for the withdrawal.

For subjects not reporting 12-month occlusion data, the 180-day efficacy outcomes will be used to impute 12-month efficacy results. A conditional analysis will be performed to determine the probability of 12-month efficacy (success, failure) based on 180-day efficacy (success, failure).

Tipping point analyses will be performed to include data on subjects without the primary safety or efficacy endpoints (missing data or subjects lost to follow-up).

7.4 CENTER HETEROGENEITY

To assess consistency of treatment effect size across study centers, any study center with less than 5 subjects will be pooled with other such study centers prior to carrying out this assessment.

A number of measures have been taken to assure center heterogeneity:

- the study sites were monitored for protocol compliance,
- the same data gathering instrument and method were used in every site.
- investigators are selected for their experience and ability in performing interventional neurovascular procedures
- investigational sites are required to follow the same detailed protocol with explicit inclusion and exclusion criteria
- the primary safety and efficacy endpoints of this study are objective events determined by a central CEC and independent angiographic core laboratory.

An analysis of comparability across study sites will be carried out to determine the similarity of study sites with respect to important demographic and other variables, either known or suspected to have an influence on the outcome variables.

Individual data, for individual k will be assumed to follow a Bernoulli distribution:

$$Y[k] \sim \text{dbern}(p[\text{center}[k]])$$

where center is an index variable that indicates the center that the individual k was recruited in. Statistical testing will be performed using Pearson's chi-square test.

7.5 SUBGROUP ANALYSIS

Subgroups for secondary analysis of primary endpoints (safety and efficacy) include:

- Location (anterior, posterior)
- Age (<60, 60-69, ≥ 70)
- Gender: results will be stratified by gender
- Anatomic location (zone 1, 2 and 3)
- Vascular risk factor: Hypertension (Yes, No)
- Vascular risk factor: Hyperlipidemia (Yes, No)
- Vascular risk factor: Tobacco Use (Yes, No)

The success percents for primary endpoints will be presented descriptively within each subgroup and global tests of significance on the endpoints will be performed to check the heterogeneity of differences in the primary endpoint success percents for safety and efficacy across all subgroups.

The purpose of this analysis is not to formally assess success within each subgroup, but simply to assess consistency of results across the various subgroups.

7.6 SECONDARY ENDPOINT VARIABLES

A Bayesian analysis will be employed in assessment of secondary endpoints.

For all dichotomous secondary endpoints, the model employed to summarize the rate (π) of secondary endpoint will be similar to the model employed for the analysis of the primary endpoints. More specifically, under the prior for the rate

$$\pi \sim \text{Beta}(1,1)$$

the posterior distribution for the secondary endpoint event rate will be

$$\pi | Y, n \sim \text{Beta}(1 + Y, 1 + n - Y)$$

where n is the number of evaluable subjects and Y is the number of subjects with events. The rate of the endpoint with a 95% credible interval will be reported; both one-tailed and two-tailed intervals will be computed to be consistent with the two OPC sets. In addition to the results based on the model, raw counts and proportions will be reported.

For all continuous secondary endpoints, the Bayesian model employed to summarize the mean outcome (μ) and standard deviation (σ) of secondary endpoint will use a conjugate analysis where the point and interval estimates are numerically the same as the sample mean and sample standard deviation. More specifically, the prior for the mean and variance will be

$$p(\mu, \sigma^2) \propto \sigma^{-2}$$

the posterior distribution for the secondary endpoint mean (μ) and variance (σ^2) will be

$$\mu | Y_1, Y_2, \dots, Y_n, \sigma^2, n \sim \text{Normal} \left(\bar{Y}_n, \frac{\sigma^2}{n} \right)$$

$$\frac{(n-1)S^2}{\sigma^2} | Y_1, Y_2, \dots, Y_n, n \sim \chi^2(n-1)$$

where n is the number of evaluable subjects and Y_1, Y_2, \dots, Y_n are the data collected on the n subjects and S^2 is the sample variance. The mean and standard deviation rate of the posterior distribution of the mean and variance of the secondary endpoint with an equitailed 95% credible interval will be reported.

